9.2.2 Assessment of secondary outcomes

The secondary outcomes will be measured as described for the primary endpoint.

Secondary smoking cessation outcome will be measured with a self-reported 7-day point prevalence abstinence (not having smoked cigarettes within the preceding week), again all confirmed by the exhaled CO level, urinary level of cotinine and anabasine, and change in the self-reported number of cigarettes smoked per day (CPD) with 50% reduction in CPD from baseline to follow-up considered as successful reduction, measured as above.

Respiratory symptoms will be assessed by questionnaires:

- COPD Assessment Test (CAT), Modified Medical Research Council (MMRC) Scale, Asthma Test (ACT/ ECRHS)

Each Urine sample will be split into six aliquots to quantify cotinine and anabasine (see above), PAH metabolites, VOCs, propylene glycol, TSNAs, 8-OHdG and 8-isoprostanes, since no analytical method can measure all the compounds together. The different compounds will be estimated as follows:

- Concentrations of urinary cotinine and anabasine, VOCs, TSNAs and PAHs will be measured for all participants
- Oxidative stress will be assessed by quantifying 8-OHdG and 8-isoprostane concentrations in both EBC and urine
- We will adapt the method for analyzing urinary TSNAs from Xia et al.[29] After enzymatic hydrolysis with a β -glucuronidase solution, the urine sample will be extracted using solid phase extraction (SPE) columns, and analyzed by LC/MS/MS.
- We will use a high performance liquid chromatography (HPLC) method developed by the IST laboratory to analyze PAHs (1- and 2-Naphtol and urinary 1-OHP).

Exhaled breath condensates (EBC) other than CO will be performed in all participants at the Lausanne site during the first as well as the outcome visit (baseline and 6 months), based on guidelines from the American Thoracic Society (ATS)/European Respiratory Society (ERS) Task Force for EBC collection[62]. EBC will be sampled with an EcoScreen II system (total exhaled volume of about 120 L). After collection, each sample will be aliquoted. To avoid auto-oxidation of fatty acids (potential impact on 8-isoprostane levels), we will add tert-butyl hydroxytoluene and rapidly freeze the sample. The samples will be stored at -70°C for a maximum of 1 month.[65]

OHdG and 8-isoprostane will be simultaneously determined in EBC, using a method adapted to Syslova et al.[65] After adding internal standards (isotopically labeled 8-OHdG and 8 isoprostane), 1 ml of EBC will be lyophilized and the residue dissolved in a water:methanol solution and immediately analyzed by a liquid chromatography–atmospheric pressure ionization tandem mass spectrometry (LC-ESI-MS/MS) method available at IST.

Cardiovascular risk factors (CVRF) will be assessed as follows:

- Blood collection: We will measure cardiovascular risk factors in blood by routine methods in clinical practice: : Total-, LDL- and HDL-cholesterol, blood glucose, triglycerides, HbA1c and creatinine.
- Blood pressure and heart rate will be measured by standard sphygmomanometer. After a 10-minute rest, the right arm blood pressure of a seated participant will be assessed at three one-minute intervals. The two final blood pressures will be averaged to reduce variability.
- Height, weight (calculation of body mass index, BMI), and abdominal circumference

Several questionnaires will be used to assess further parameters:

- Demographics: Age, gender; Socio-economic: education level, marital status; medical history, including medication use and healthcare utilization.

- Smoking history,[90, 91] including Fagerström questionnaire to assess nicotine dependence[92] and the Minnesota nicotine withdrawal scale.[93]
- Physical activity (International Physical Activity Questionnaire, IPAQ) [77]
- legal and illegal drug use: Alcohol consumption (AUDIT-C) [80, 94], illegal drug use (cannabis, cocaine, other) [81]
- Quality of life (EQ-5D questionnaire)[83]
- Depression symptoms (PHQ-9)[95]
- Anxiety (GAD-7) [85]
- Sleep Quality (PSQI) [82]
- Environmental pollution exposure (e.g. second hand smoke) [86, 87]

9.2.3 Assessment of other outcomes of interest

See above.

9.2.4 Assessment of safety outcomes

Information on safety outcomes (AEs of special interest, SAEs, visits to the family practitioner, in-patient hospitalizations / prolongation of existing hospitalizations), and ENDS deficiencies will be collected proactively during the phone calls and the 6-months in person visit using standardized questionnaires and international guidelines.[88]

9.2.4.1 Adverse events

For this trial, AEs of special interest as well as all SAEs will be collected, fully investigated, and documented in the source documents and the eCRF for all participants from the date of ICF signature until the last protocol-specific procedure has been completed. AEs of special interest include dry mouth, cough/dry cough, shortness of breath (dyspnea), throat / mouth irritation, headache, dizziness and increased heart rate / palpitations.

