7.4 Criteria for withdrawal / discontinuation of participants

Discontinuation of treatment

Treatment will be discontinued if:

- A participant reports she is pregnant.

Treatment may be discontinued if:

- Participants do not comply with the instructions by the research team;
- A treatment-related SAE is suspected;
- The protocol has been irretrievably violated, as determined by the sponsor.

Subjects who permanently discontinue study treatment are encouraged to continue in the follow-up period and to attend the protocol-specified follow-up visit at 6-, 12- and 24- month follow-up visits in accordance with the intention-to-treat principle.

Discontinuation of participation in the study

Participation in the trial will be stopped if:

- participants make a request to discontinue their participation

Participation in the trial may be stopped if:

- the responsible study investigator decides that continued participation in the study could be harmful to the subject's wellbeing

A participant who decides to discontinue the study participation prematurely will be defined as a dropout if he/she has already been randomized. A study participant who terminates the study before being randomized will be defined as a screening failure.

Participants who cannot be reached over the phone at follow-up visits will not be excluded. Participants who do not present at the 6/12/24-month visits will be contacted by phone, by letter, and, finally, we will contact two contact persons and the primary care provider listed by participants at the baseline visit. If we cannot contact participants for more than three months, we will consider them lost to follow-up.

Participants who have finished their study at 6 months according to their signed informed consent will be contacted by phone or by e-mail to ask if they would like to continue their study participation for the 12- and 24-months visit. If they don't wish to continue or if they are unreachable no further contact attempts will be performed. These participants will be considered as having finished the study according to the protocol.

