9.2.4.1 Adverse events

For this trial, all AEs as well as all SAEs will be collected, fully investigated, and documented in the source documents and the eCRF for all participants from the date of ICF signature until the last protocol-specific procedure has been completed.

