10.4 Other clinical trial Category B

During the entire duration of the study, all adverse events (AE) and all serious adverse events (SAEs) are collected, fully investigated and documented in source documents and case report forms (eCRF). Study duration encompassed the time from when the participant signs the informed consent form until the last protocol-specific procedure has been completed.

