11.4.5 Safety analysis

We will compare the proportion of adverse events and serious adverse events between groups using recommended methods.

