October 10 th , 2019 / November 26 th 2019	Approval of changes: 
 1. Study site Zürich (Nov 26th) and St-Gallen (Oct 10th). 2. Extension of follow-up to 12- and 24-months. 3. Vouchers to control group given at baseline instead of giving them the voucher after completion of the 6-months visit. 4. Adaptations of documentation of Adverse Events 	Protocol version 7.0, Dated September 10 th , 2019. 
 1. Extension of recruitment to study site Zürich and St-Gallen to meet recruitment targets. 2. Additional funding obtained by Tobacco Prevention Fund and Swiss Cancer Research enabling extension of follow-up to 12- and 24-months follow-up 3. We noticed selective attrition through withdrawal in the control group. We decided the control group should receive a voucher at baseline instead of 6-months follow-up to mitigate deception in control group. 4. Further adaptations in documentation of AE by study nurses with systematic queries to hospitals and attending physicians in case of AE and not only SAE
October 11 th , 2019	Information to CEC related to EVALI epidemic in USA: 
 1. Letter sent to all participants asking them to report any respiratory symptoms 	
 1. In light of the reports in the USA about EVALI cases, the research team reviewed already collected SAE and AE, reviewed the literature and reports coming out of the USA and decided to pursue the study as planned. We sent a letter to participants informing them about the situation in the USA, which was most likely due to use of illicit e-liquids or e-liquids used for vaping cannabis and that they should continue to report adverse events to study nurses. 2.
March 2020, until July 2020	Incremental lockdown measures related to COVID pandemic decided by Federal Council of Switzerland. 
 1. Pause in recruitment of new participants from: March to July 2020 2. Shift as much as possible clinical follow-up visit from in-person visits to phone follow-ups. 	
 1. COVID pandemic required us to pause recruitment of new participants. 2. Study nurses continued to follow-up participants at scheduled times over the phone, following up participants in person if allowed locally.

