6.6 Safety evaluation

Safety outcomes will be analysed using the ITT and PP set.

The safety analysis will list the number of patients dropping out for both treatment arms, including the reasons, and a list of events for patients dropping out, with the treatment group, relation, grade, type of AE and potential free text.

AEs and SAEs will be summarized by presenting for both treatment arms the number of any AE, any SAE, and the number and percentage of patients with any AE or any SAE.

Further, we will present the

- grade and relation of AEs and SAEs (number of patients with events and the number of events),
- category and grade of AEs and SAEs
- category and relation of AEs and SAEs
- AEs and SAEs stratified by consumption (cigarettes, ENDS, both, none)

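### Adverse events are compared by arm as plain counts and percentages, with no onset window and no person-time, although observed time may differ between arms

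*Supplement*

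**What the plan says.** Protocol 9.0, section 9.2.4.1, has all AEs and SAEs recorded "for all participants from the date of ICF signature until the last protocol-specific procedure has been completed". Section 10.4 repeats the window: "Study duration encompassed the time from when the participant signs the informed consent form until the last protocol-specific procedure has been completed". The visit schedule now includes months 6, 12 and 24, and AEs are asked about at each.

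Section 7.4 makes the end of that window differ between people. "Participants who have finished their study at 6 months according to their signed informed consent will be contacted by phone or by e-mail" to ask whether they will go on to months 12 and 24; "if they are unreachable no further contact attempts will be performed". Those who do not go on count as having completed the study.

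For the analysis, protocol 11.4.5 says: "We will compare the proportion of adverse events and serious adverse events between groups using recommended methods". SAP 2.0 section 6.6 gives, for each arm, "the number of any AE, any SAE, and the number and percentage of patients with any AE or any SAE", with breakdowns by grade, relation, category and consumption. Section 4.2.3 names the ITT and PP sets and sets no time limit. Section 6.1 lists AEs and SAEs among the core secondary outcomes, but Table 3, which derives the other outcomes visit by visit, has no row for them.

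Sections 2.6 and 2.7 of the SAP place the analysis after completion of 6-month follow-up, assess secondary outcomes at month 6 and leave 12- and 24-month outcomes out.

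The history of changes, in the entry for Protocol 7.0, records: "We noticed selective attrition through withdrawal in the control group".

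**The concern.** An adverse event is not a measurement taken at one visit. Events accumulate, so a count or a percentage with any event depends on how long each person was observed. The SAP says which visit its outcomes belong to, but not which event dates enter the safety tables, and it gives no denominator of time.

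If the arms are observed for equal time on average, this does little harm to the comparison. If controls are observed for less time, a percentage of all randomised controls misses events that happened after they left. ENDS then appears to cause more events than it does, or a true reduction on ENDS is partly cancelled. The trial is open label, safety is a stated objective, and the sponsor itself saw withdrawal concentrated in the control arm.

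**Working it through.** The plan gives no AE rate, no follow-up time by arm and no power for safety, so there is no figure of its own to reproduce. The steps below show how the planned tables behave when the true risk is the same in both arms. All AE risks, attrition shares and continuation shares are assumptions.

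**Inputs from the documents.** 586 per arm (protocol 6.1); baseline visit 7 days before the target quit date; 6-month visit at day 180 with a window of −4/+12 weeks; 24-month visit at day 720; two-sided 5% level (SAP 4.1).

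**Step 1: spread within the 6-month visit.** 180 − 28 = 152 and 180 + 84 = 264 days from target quit date, as in SAP Table 1. From baseline this is 159 to 271 days, a ratio of 271/159 = 1.70. With a constant hazard and a 30% risk at 187 days (180 + 7), the chance of any event is 26.2% at 159 days and 40.4% at 271 days. An undefined cut-off of the 6-month visit is therefore itself uneven.

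**Step 2: cut at 6 months, attrition differing by arm.** Let p6 = 30%, so h = −ln(0.70)/187 = 0.00191 per day. Dropouts are observed for 60 days on average, giving 1 − exp(−60h) = 10.8%. The observed percentage in an arm with attrition d is (1 − d) × 30% + d × 10.8%.

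| Attrition, ENDS vs control | Any AE, ENDS | Any AE, control | Risk ratio | Chance of a significant ENDS excess |
|---|---|---|---|---|
| 5% vs 5% | 29.0% | 29.0% | 1.00 | 2.5% |
| 5% vs 10% | 29.0% | 28.1% | 1.03 | 5.5% |
| 5% vs 15% | 29.0% | 27.1% | 1.07 | 11% |
| 5% vs 25% | 29.0% | 25.2% | 1.15 | 32% |

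For example, 0.85 × 30% + 0.15 × 10.8% = 27.1%. The last column applies a two-sided 5% two-proportion test with 586 per arm; its nominal value is 2.5%. For 6-month risks from 5% to 50%, the risk ratio stays at 1.07 to 1.08 for 5% vs 15%, and at 1.14 to 1.16 for 5% vs 25%.

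**Step 3: the same case per person-time.** Mean observed days are 0.95 × 187 + 0.05 × 60 = 180.65 on ENDS and 0.85 × 187 + 0.15 × 60 = 167.95 on control. Under one common hazard, expected event counts have the ratio 180.65/167.95 = 1.08. Divided by person-time, the ratio is 1.00.

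**Step 4: what if later events were also counted.** Observation from baseline is 187 or 727 days (720 + 7), a ratio of 3.9. With a 10% risk at 6 months, the 24-month risk is 1 − 0.90^(727/187) = 33.6%. If 60% on ENDS and 50% of controls were followed to month 24, the percentages would be 24.2% and 21.8% (risk ratio 1.11). With 70% and 50% they would be 26.5% and 21.8% (1.22). With equal shares the ratio is 1.00, however mixed the follow-up.

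**The case against.** The strongest reply is that the SAP already has a 6-month scope. AEs and SAEs are core secondary outcomes, secondary outcomes belong to month 6, and the 12- and 24-month outcomes are excluded. This stands. A reader might infer that the safety tables will mix 6-month and 24-month observation; the documents do not say so. Nor does the 2023 date of SAP 2.0, which is later than the planned last participant out (05/22), show that later events enter these tables. They would enter only if the data export were not cut by onset date. What the reply leaves open is that the scope is never written as a rule for which events count.

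Second, mixed follow-up is not a bias under 1:1 randomisation unless it differs by arm. This also stands. The recorded control-arm withdrawal was noted in the amendment that first added the 12- and 24-month visits, so it concerns the 6-month phase and says nothing about uptake of the extension. The same amendment moved the control voucher to baseline as a countermeasure, and the protocol projects equal losses of 5%, 7% and 10% in both arms. Large false-positive rates can be produced by assuming that continuation to 24 months differs by arm, but no document supports a particular gap. The withdrawal within 6 months is, however, on record, and its remaining size is unknown.

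Third, SAP 5.7 tabulates non-completion by arm and time point, and 6.6 lists dropouts with reasons, so unequal follow-up would be visible. Visible is not adjusted for: the percentages would still have all randomised as denominator. The censoring weights in SAP 6.5 are not tied to the tables in 6.6, where someone who left early without an event simply counts as event-free.

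Fourth, 6.6 is descriptive, and the wording of 11.4.5 does not rule out exposure-adjusted methods. True, but neither section commits to them.

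**Conclusion.** The point holds in a limited form. The collection window is open-ended, the 6-month scope is not turned into an onset rule, and the between-arm summary takes no account of observed time. With the selective control-arm withdrawal on record, plain percentages of all randomised would undercount control-arm events and could create a false ENDS excess or otherwise distort the comparison.

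The size cannot be known from the documents. Under a constant and equal hazard, with a 30% 6-month risk and dropouts seen for 60 days, it is a risk ratio of about 1.07 at 5% vs 15% attrition and 1.15 at 5% vs 25%. It would be larger if events after month 6 were counted and continuation differed by arm, for which there is no evidence either way.

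This is a cheap improvement to the safety analysis. It concerns the between-arm tables, not the tables by consumption, and does not touch the primary outcome.

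**What to change.** In SAP 6.6, and in matching words in protocol 11.4.5:

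- For the 6-month safety tables, count AEs and SAEs by onset date in one common window ending on a fixed day, and state the day and its origin (randomisation or target quit date).
- Censor each participant at last contact if that comes earlier.
- Report person-time and event rates per person-month by arm beside the counts and percentages.
- Put later events in a separate table, also per person-time.

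The cost is one SAP paragraph and one derived variable. The last-contact date is already in the end-of-study form (SAP 5.7); onset dates are assumed to be in the eCRF. No new data are needed. One consequence should be accepted openly: events with onset after the fixed day but reported at a late, in-window 6-month visit move to the later table. Person-time corrects for unequal length of observation, not for withdrawal that is itself linked to the risk of an event, so the dropout listing by arm remains useful.

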9.2.4.2 Laboratory parameters

See above (assessment of secondary outcomes)

9.2.4.3 Vital signs

See above (assessment of secondary outcomes)

9.2.5 Assessments in participants who prematurely stop the study

Subjects who permanently discontinue study treatment are encouraged to continue in the follow-up period and to attend the protocol-specified follow-up visit at 6 months in accordance with the intention-to-treat principle.

9.3 Procedures at each visit

9.3.1 Screening phone call at -x to -8 days to target quit date:

- Study information and explanation
- Eligibility check (inclusion/exclusion criteria)
- Scheduling of target quit date and baseline visit
- Smoking history

9.3.2 Visit 1, Baseline visit at -7 days to target quit date

- Patient information and delivery of written study information to subject
- Verification of eligibility, including urine pregnancy test for premenopausal women
- Informed consent
- Demographics
- Relevant medical history including current medication
- Smoking history and symptoms linked to smoking, nicotine dependence (Fagerström questionnaire), withdrawal symptoms
- Body weight, height, calculation of BMI, waist circumference

- Vital signs (heart rate, systolic and diastolic blood pressure at the right arm after at least 5 minutes at rest)
- Questionnaires
 - Respiratory symptoms
 - Quality of life
 - Physical activity
 - Anxiety
 - Depression
 - Sleep quality
 - Alcohol and illegal drug use
 - Environmental pollution exposure
- Exhaled breath composition (CO, oxidative stress markers in a subset of participants)
- Blood collection (lipids, glucose, HbA1c & creatinine)
- Urine collection (nicotine metabolites, VOCs, PAHs, nitrosamines, oxidative stress markers)
- Randomization to study group
- Distribution and instruction of ENDS and e-liquids (intervention group only)
- Smoking cessation counselling
- Scheduling of phone calls

9.3.3 Phone calls at target quit date, week 1, week 2, week 4, and week 8

Phone calls at target quit date (corresponding to day 0) and after 1 week (± 2 days), 2 weeks (± 3 days), 4 weeks (± 4 days), and 8 weeks (± 1 week):

- Smoking status: cigarettes / ENDS
- Assessment of other NRT use
- Assessment of SAE and AEs of special interest
- Smoking cessation counselling
- ENDS technical trouble shooting
- Scheduling of phone calls and outcome visit

9.3.4 Outcome visit (month 6)

Visit at 6 months (corresponding to 24 weeks (-4 weeks/+12 weeks) after the target quit date):

- Current medication
- Smoking status, nicotine dependence (Fagerström questionnaire), withdrawal symptoms
- Assessment of AEs of special interest
- Body weight, height, calculation of BMI, waist circumference
- Vital signs (heart rate, systolic and diastolic blood pressure at the right arm after at least 5 minutes at rest)
- Questionnaires
 - Respiratory symptoms
 - Quality of life
 - Physical activity
 - Anxiety
 - Depression
 - Sleep quality
 - Alcohol and illicit drug use
 - Environmental pollution exposure
- Exhaled breath composition (CO, oxidative stress markers in a subset of participants)
- Blood collection (lipids, glucose, HbA1c & creatinine)
- Urine collection (nicotine metabolites, VOCs, PAHs, nitrosamines, oxidative stress markers)
-

10. SAFETY

10.1 Drug studies

Not applicable

10.2 Medical Device Category C studies

Not applicable

10.3 Medical Device Category A studies

Not applicable

10.4 Other clinical trial Category B

During the entire duration of the study, all adverse events (AE) of special interest (see section 9.2.4.1) and all serious adverse events (SAEs) are collected, fully investigated and documented in source documents and case report forms (eCRF). Study duration encompassed the time from when the participant signs the informed consent form until the last protocol-specific procedure has been completed.

10.4.1 Definition and assessment of (serious) adverse events

An **AE** is any untoward medical occurrence in a clinical investigation participant administered an intervention and which does not necessarily have a causal relationship with the intervention. An AE can therefore be any unfavourable and unintended sign (including an abnormal laboratory finding), symptom, or disease temporally associated with the intervention, whether or not related to the intervention. [ICH E6 1.2, adapted]

A **SAE** is classified as any event which:

- requires inpatient treatment not envisaged in the protocol or extends a current hospital stay;
- result in permanent or significant incapacity or disability;
- is life-threatening or results in death; or
- causes a congenital anomaly or birth defect.

In addition, important medical events that may not be immediately life-threatening or result in death, or require hospitalisation, but may jeopardise the patient or may require intervention to prevent one of the other outcomes listed above should also usually be considered serious.

SAEs should be followed until resolution or stabilisation. Participants with ongoing SAEs at study termination will be further followed up until recovery or until stabilisation of the disease after termination, or until the participant is lost to follow-up.

Assessment of Causality

The assessment of causality of SAEs will be done by both, investigator and Sponsor-Investigator based on the criteria listed in the ICH E2A guidelines:

Relationship	Description
--------------	-------------

Definitely	Temporal relationship Improvement after dechallenge* Recurrence after rechallenge (or other proof of drug cause)
Probably	Temporal relationship Improvement after dechallenge No other cause evident
Possibly	Temporal relationship Other cause possible
Unlikely	Any assessable reaction that does not fulfil the above conditions
Not related	Causal relationship can be ruled out
*Improvement after dechallenge only taken into consideration, if applicable to reaction	

Assessment of Severity

Classification and severity grading scale in this study will be performed in accordance with “Common Terminology Criteria for Adverse Events CTCAE Version 4.03” terminology.

